**DEVICE NAME:**  
HOFFMANN® LRF SYSTEM  
SALVATION™ EXTERNAL FIXATION SYSTEM  
SALVATION™ FUSION BOLTS AND BEAMS  
SALVATION™ 2 MIDFOOT NAIL  
SALVATION™ 3DI PLATING SYSTEM  
T2® ICF SYSTEM  
VALOR™ ANKLE FUSION NAIL SYSTEM

**CLINICAL INVESTIGATION DESIGN:** Prospective, multi-site, multi-year post-market clinical follow-up study

**INDICATIONS:** This clinical investigation will adhere to the indications and contraindications for the systems under investigation, as detailed in the devices' Instructions for Use (IFU) and Surgical Technique Manual.

**CLINICAL INVESTIGATION PLAN PHASE:** Post-Market Clinical Investigation

## 1. List of Abbreviations

Acronym	Definition
AE	Adverse Event
CFR	Code of Federal Regulations
CI	Confidence Interval
CIP	Clinical Investigation Plan
CRF	Case Report Form
CV	Curriculum Vitae
eCRF	Electronic Case Report Form
EC	Ethics Committee
EDC	Electronic Data Capture
EQ-5D	A standardized health-related quality of life instrument by the EuroQuol Group
FAAM	Foot and Ankle Ability Measure
FDA	Food and Drug Administration
ICF	Informed Consent Form
ICH-GCP	International Conference of Harmonisation Good Clinical Practice
ID	Investigation Device
IFU	Instructions for Use
IRB	Institutional Review Board
LTFU	Lost to Follow-Up
PG	Performance Goal
PI	Principal Investigator
Pre-Op	Pre-Operative
PROM	Patient Reported Outcome Measure
SAE	Serious Adverse Event
SAP	Statistical Analysis Plan
UADE	Unanticipated Adverse Device Effect

## 2. Synopsis

Title	Lower Extremity Fixation In Neuropathic Patients Study (FINS)
Treatment	HOFFMANN® LRF SYSTEM SALVATION™ EXTERNAL FIXATION SYSTEM SALVATION™ FUSION BOLTS AND BEAMS SALVATION™ 2 MIDFOOT NAIL SALVATION™ 3DI PLATING SYSTEM T2® ICF SYSTEM VALOR™ ANKLE FUSION NAIL SYSTEM
Design	Prospective, multi-site, multi-year post-market clinical follow-up study
Objective	The primary objective of this study is to compare the pooled cumulative 3-year amputation rate to a performance goal derived from a literature-based source.
Endpoints	
Primary Endpoint:
 
 
Performance or survival of the device measured as the 3-Year Amputation Rate.
 
 
Secondary Endpoints:
 
 
Evaluate the change in patient-report of pain, function, and social interaction for quality of life from pre-op through each annual visit as assessed by the EQ-5D-5L, the FAAM and its component scores.
 
Safety of the implants in terms of complications and adverse events through 5 years.
 
Investigator assessment of the implant including radiographic assessment of deformity correction, and fusion/consolidation time through 1 Year.
 
Performance or survival of the device measured as the 5-year Amputation Rate.
 

Target Population	Approximately 200 subjects are to be enrolled in this clinical investigation at approximately 10 sites. Enrolled subjects will be assessed at Pre-Operative, Operative/Discharge, 6 Months, 1 Year, 2 years, 3 Years, 4 Years and 5 Years after the index procedure.
Inclusion Criteria	
 
Subject is a male or non-pregnant female age 18 years or older at the time of surgery;
 
Subject is willing and able to give written informed consent and comply with the requirements of this Clinical Investigation Plan; and
 
Subject has neuropathy and is intended to be treated for deformity with the one or a combination of the below Systems in accordance with the legally cleared/approved IFU and Surgical Technique Manual. 
 
HOFFMANN® LRF SYSTEM
 
SALVATION™ EXTERNAL FIXATION SYSTEM
 
SALVATION™ FUSION BOLTS AND BEAMS
 
SALVATION™ 2 MIDFOOT NAIL
 
SALVATION™ 3DI PLATING SYSTEM
 
T2® ICF SYSTEM
 
VALOR™ ANKLE FUSION NAIL SYSTEM
 
 
 

Exclusion Criteria	

a. Subjects determined, by the investigator, to be an inappropriate candidate for the procedure indicated;

b. Unable to consent to participate (written, informed consent);

c. Unable to attend/complete the requested follow-up visits.

--------------------	--

#### 3.3 EDC SYSTEM

Information on file at the Sponsor

### 4 Product Information

All components of the HOFFMANN® LRF SYSTEM, SALVATION™ EXTERNAL FIXATION SYSTEM, SALVATION™ FUSION BOLTS AND BEAMS, SALVATION™ 2 MIDFOOT NAIL, SALVATION™ 3DI PLATING SYSTEM, T2® ICF SYSTEM, and VALOR™ ANKLE FUSION NAIL Systems were cleared and approved for sale and use prior to starting the clinical investigation.

These Systems are to be used only for indications for which they have been approved. Please see the approved IFUs and Surgical Technique Manuals for a detailed description of the medical device(s) and instrumentation and intended use information.

Medical device product traceability will be achieved by capturing the implant lot number.

## 5 Risks and Benefits

This prospective, multi-center, clinical investigation is designed to examine the safety and efficacy/performance of the HOFFMANN® LRF SYSTEM, SALVATION™ EXTERNAL FIXATION SYSTEM, SALVATION™ FUSION BOLTS AND BEAMS, SALVATION™ 2 MIDFOOT NAIL, SALVATION™ 3DI PLATING SYSTEM, T2® ICF SYSTEM, and VALOR™ ANKLE FUSION NAIL Systems, in accordance with the approved IFU, labeling and instrumentation. The potential risks to subjects are described in the approved IFUs and Surgical Technique Manuals. There are no additional risks anticipated, specific to participating in this study. The study is not examining any experimental procedures and participation in the study is not predicted to affect the medical treatment received by enrolled subjects

This is an observational study, so participation may not result in direct benefit to the subject. The use of information contained within the database may be of future benefit to subjects undergoing certain orthopedic procedures.

## 6 Introduction

Stryker introduced multiple devices to treat deformity in the neuropathic patient (lack of sensation with the 10 gram Semmes Weinstein monofilament) population. All of the devices have been cleared by the FDA. See below for the list of devices, dates of clearance, and FDA 510K numbers.

Device Name	Date of Clearance	510K Number
HOFFMANN® LRF SYSTEM	01Feb2021	K203568
SALVATION™ EXTERNAL FIXATION SYSTEM	06Jun2018	K180832
SALVATION™ FUSION BOLTS AND BEAMS	21Mar2014	K140741
SALVATION™ 2 MIDFOOT NAIL	11Jul2018	K180024
SALVATION™ 3DI PLATING SYSTEM	22May2014	K140792
SALVATION™ OSTEOPENIC SCREW	14May2014	K140408
T2® ICF SYSTEM	20Mar2020	K193366
VALOR™ ANKLE FUSION NAIL	22Oct2014	K142602

Table 6.1 Study Device FDA 510K Clearance Information

The primary outcome measure of this study will compare the pooled cumulative 3-year amputation rate derived from a Kaplan-Meier survival analysis to a performance goal derived from a literature-based source. Descriptive analyses will then compare survival curves in patients for specific devices over the entire 5-year follow-up period. Secondary endpoints include improvements in patient-reported pain, function, and social interaction for quality of life from pre-op through each annual visit as assessed by the EQ-5D-5L and the FAAM and its component scores. As well as investigator assessment of the implant including radiographic assessment of deformity correction, and fusion/consolidation time through 1 Year

The outcome measures collected in this study will be analyzed and reported as required for local, regional, and country requirements (i.e., regulatory authorities and notified bodies).

## 7 Clinical Investigation Design

This investigation is a prospective, multicenter post-market clinical follow-up study. It is anticipated that a total of 200 subjects meeting all the eligibility criteria will be enrolled at approximately 10 sites. The enrollment period is expected to occur over 48 months. Total duration of enrollment, 5 years follow-up of subjects, and data analysis is expected to take 9 years.

The study treatment is approved for use and conforms to regulatory requirements. This investigation employs these procedures and devices for uses that are consistent with their regulatory cleared/approved labeling. The clinical investigation was designed to follow the surgeon's standard of care for treatment of deformity in the neuropathic patient in addition to annual follow-up visits through 5 years. Neither subjects nor investigators are blinded to treatment.

### 7.1 CLINICAL INVESTIGATION RATIONALE

The Sponsor has identified the need to collect post-market clinical follow-up data to verify the safety and efficacy/performance of the HOFFMANN® LRF SYSTEM, SALVATION™ EXTERNAL FIXATION SYSTEM, SALVATION™ FUSION BOLTS AND BEAMS, SALVATION™ 2 MIDFOOT NAIL, SALVATION™ 3DI PLATING SYSTEM, T2® ICF SYSTEM, and VALOR™ ANKLE FUSION NAIL Systems. The Sponsor believes that a prospective, multi-center, post-market clinical follow-up study evaluating the on-label usage of these Systems is the most appropriate way to capture this type of data.

The primary and secondary endpoints will be used to demonstrate safety and performance/efficacy of these Systems. Efficacy will be assessed through comparing the pooled cumulative 3-year amputation rate derived from a Kaplan-Meier survival analysis to a performance goal derived from a literature-based source. Safety will be assessed through the incidence of device related intra-operative and post-operative adverse events/incidents (AEs) by 5 years.

All subjects will be followed in accordance with the Investigator's standard-of-care, with additional annual follow-up visits through 5 years. These visits may be considered outside of standard-of-care for some surgeons; however, it is necessary to provide a full assessment of the primary endpoint measure.

## 8 Objective

The primary effectiveness hypothesis is that the 3-year amputation rate (including both above and below the knee) is less than the performance goal (PG).

The PG was based on data summarized in Elmarsafi et al 2019. This study summarized patients with diabetic Charcot neuroarthropathy (CN). The aim of this study was to identify risk factors for major lower extremity amputations among patients who underwent osseous Charcot reconstruction. A retrospective review was performed on 331 patients with the diagnosis of CN in the foot and ankle treated over a 16-year period. Two hundred eighty-five patients were included after exclusion of those without diabetes.

Among N=285 patients, n=49 (17.2%) experienced an amputation with mean follow-up of 29.5 months (range 12.1 to 124.4). The sample estimate to be compared to the PG is the 36-month cumulative amputation rate and so is conservative relative to the mean 29 months of follow-up in the Elmarsafi et al 2019 study.

In order to derive a PG amenable to statistical testing, a small reference margin of 3% will be used. This represents a 17.4% increase above the literature-based value of 17.2%. Adding a reference margin allows there to be non-trivial power if the true event rate is at least moderately less than 17.2%. Therefore, PG is defined as  $17.2\% + 3\% = 20.5\%$ . If the upper bound of a one-sided 95% CI for the 3-year cumulative amputation rate as determined Kaplan-Meier analysis is less than 20.5%, the PG will be met.

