4.1 Background and Rationale

This statistical analysis plan is developed to provide the analytic framework and the production of statistical output of the FIN Study. This analysis plan is based on the FINS CIP version 3, dated 27 April 2022. The FIN Study was a prospective, multisite, multiyear, post-market follow-up clinical (PMCF) investigation that aimed to compare the pooled three-year amputation rate of the investigational devices in **Table 1** to a performance goal derived from a literature-based source. The study planned to enroll at least 200 subjects at 10 sites in the US, however, the Sponsor decided to discontinue the enrollment on 28 October 2022. Approximately 42 subjects were implanted with at least one investigational device when the study was discontinued. This statistical plan will guide the statistical analysis and presentation of these subjects that were enrolled and implanted with any of the devices under investigation.

Table 1. Study Device FDA 510K Clearance Information

Device Name	Date of Clearance	510K Number
HOFFMANN® LRF SYSTEM	01Feb2021	K203568
SALVATION™ EXTERNAL FIXATION SYSTEM	06Jun2018	K180832
SALVATION™ FUSION BOLTS AND BEAMS	21Mar2014	K140741
SALVATION™ 2 MIDFOOT NAIL	11Jul2018	K180024
SALVATION™ 3DI PLATING SYSTEM	22May2014	K140792
SALVATION™ OSTEOPENIC SCREW	14May2014	K140408
T2® ICF SYSTEM	20Mar2020	K193366
VALOR™ ANKLE FUSION NAIL	22Oct2014	K142602

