6.6 Sample Size

The study required a sample size of 141 patients to provide at least 80% statistical power to reject the hypothesis that the 3-year amputation rate is less than the PG with a significance $\alpha=0.05$. However, this sample size requirement was not met at study discontinuation.

7 General Analysis Considerations

Data will be summarized for each of the devices listed in **Table 1**. Because the study was prematurely terminated, all analysis will be descriptive only. All analyses will be done to summarize all available data. No statistical hypothesis testing will be implemented.

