9.1 Primary Effectiveness/Performance Analysis

None of the subjects reached their three-year post-surgery follow-up. Thus, the three-year amputation rate, which is the primary endpoint will not be analyzed. Instead, the frequency of amputations at each post-surgery visit will be presented. The status of the subject at the latest follow-up, coded as either walking, use of mobility aids, bedridden or having amputation will be summarized instead.

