10.2 Serious Adverse Events

A separate summary table (or listing) of complications that met the serious adverse events (SAE) classification will be presented. Also, this section presents the narratives of each SAE that occurred in the clinical investigation. A serious adverse event (SAE) as defined from ISO 14155:2020(E) Clinical Investigations of Medical Devices for Human Subjects - Good clinical practice, is any adverse event that:

- a. Led to death,
- b. Led to a serious deterioration in the health of the subject, that either resulted in

- A life-threatening illness or injury, or
- A permanent impairment of a body structure or a body function, or
- In-patient or prolonged hospitalization, or
- Medical or surgical intervention to prevent life-threatening illness or injury or permanent impairment to a body structure or a body function.

c. Led to fetal distress, fetal death or congenital abnormality or birth defect.

The narrative for each SAE will be presented to describe the following:

- Nature and intensity of the event,
- Clinical course leading up to the event,
- Indication of timing relevant to test investigational device/product administration,
- Relevant laboratory measurements;
- Whether the treatment was stopped, and countermeasures (and timing);
- Post-mortem findings;
- Investigator's opinion on causality and sponsor's opinion on causality, if appropriate.

In addition, the following information will be included (if available) in the SAE narrative:

- Patient identifier;
- Age and sex of patient; general clinical condition of the patient, if appropriate;
- Disease being treated (this is not required if it is the same for all patients) with duration (of the current episode) of illness;

11 Reporting Conventions

All statistical output will have the following standard elements:

Stryker Corporation
US-20-SAL-001-FINS Page of

Title of Display
Clinical investigation Population
<BODY OF DISPLAY>

12 Summary of Changes to the CIP and/or SAP

No changes to the planned statistical analysis as indicated in the CIP.

13 Statistical Software

All statistical analyses will be performed using SAS version 14.1 or higher.

14 Listing of Tables, Listings, and Figures (TLF)

The listings of TLF are provided below with the link to the corresponding Table templates in Appendix 1.

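### The performance goal is added up wrongly in CIP Section 8: 17.2% + 3% is 20.2%, not the 20.5% printed in the success criterion

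*Protocol*

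**What the plan says.** CIP Section 8 takes the PG from one published retrospective series: "Among N=285 patients, n=49 (17.2%) experienced an amputation". It then adds a margin to make the goal testable: "a small reference margin of 3% will be used. This represents a 17.4% increase above the literature-based value of 17.2"%. The next step defines the PG as 17.2% + 3% = 20.5%. The success rule repeats the figure: the goal is reached if the upper bound for the 3-year cumulative rate "as determined Kaplan-Meier analysis is less than 20.5%, the PG will be met".

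CIP Section 11.1 writes the null as an amputation rate of at least 0.202 and the alternative as a rate below 0.202. It reports 92% power with 141 subjects at a one-sided type 1 error of 0.025 and an expected rate of 10%, but does not call 0.202 the PG. CIP Section 11.2.2 and SAP Section 5 refer to the PG without a number.

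The SAP was written after enrolment ended early: "Approximately 42 subjects were implanted with at least one investigational device when the study was discontinued" (Section 4.1). Section 7 adds "No statistical hypothesis testing will be implemented", and Section 9.1 says of the primary analysis: "Thus, the three-year amputation rate, which is the primary endpoint will not be analyzed". SAP Section 12 states "No changes to the planned statistical analysis as indicated in the CIP".

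**The concern.** The printed sum is wrong, and the wrong value sits in the decision rule as well as in the derivation. The CIP therefore holds two thresholds for one hypothesis: 20.5% in the criterion for success and 20.2% in the null used for the sample size. The larger value is the easier one to meet, so the error favours the devices.

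Had the primary test been run as written, the study would have been judged against a goal 0.3 points above the one it was designed to test. Since the test has been dropped, what remains at stake is the record. A final report that describes the planned objective and takes the PG from the CIP would repeat the wrong number, because no other number carries that label.

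**Working it through.** **Inputs.** From CIP Section 8: 49 amputations among 285 patients, stated as 17.2%; margin 3 percentage points; relative increase 17.4%; PG 20.5%. From CIP Section 11.1: null rate 0.202; expected rate 0.10; unadjusted chi-square test; one-sided type 1 error 0.025; N = 141; power 92%.

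**Step 1: the sum.**
- 17.2 + 3 = 20.2.
- Rounding does not explain 20.5: 49/285 = 17.19%, and 17.19 + 3 = 20.19.
- 3/17.2 = 17.44%, which matches the stated 17.4%. Working back, 1.174 × 17.2 = 20.19.
- A PG of 20.5% needs a margin of 3.3 points, and 3.3/17.2 = 19.2%. The CIP states neither figure.

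**Step 2: the sample size.** For the one-sample chi-square (score) test with null rate p0, true rate p1 and no continuity correction,

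power = Φ{ [ (p0 − p1)√N − 1.960·√(p0(1 − p0)) ] / √(p1(1 − p1)) }

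- p0 = 0.202: (0.102 × 11.874 − 1.960 × 0.4015)/0.3 = (1.2112 − 0.7869)/0.3 = 1.414, so power is 92.1%. This reproduces the stated 92%.
- p0 = 0.205: (0.105 × 11.874 − 1.960 × 0.4037)/0.3 = (1.2468 − 0.7912)/0.3 = 1.519, so power is 93.6%, which would be reported as 94%.

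The N for 92% power is [ (1.960·√(p0(1 − p0)) + 1.405·√(p1(1 − p1)))/(p0 − p1) ]²:
- p0 = 0.202: (0.7869 + 0.4215)/0.102 = 11.847; squared 140.4, so N = 141.
- p0 = 0.205: (0.7912 + 0.4215)/0.105 = 11.550; squared 133.4, so N = 134.

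The sample size was built on 0.202.

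**Step 3: effect on the decision rule.** The CIP does not name the method for the Kaplan-Meier confidence bound, so six common methods were tried. With every subject followed for 3 years or to amputation, the Kaplan-Meier estimate is a simple proportion. The table gives the largest number of amputations that still passes, at PG 20.2% → 20.5%. Both confidence levels appear because CIP Section 8 specifies a one-sided 95% bound and Section 11.2.2 a one-sided 97.5% bound.

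| Method | N=141, 97.5% | N=141, 95% | N=200, 97.5% | N=200, 95% |
|---|---|---|---|---|
| Exact | 18 → 19 | 20 → 20 | 29 → 29 | 30 → 31 |
| Log-log | 18 → 19 | 20 → 20 | 29 → 29 | 30 → 31 |
| Wilson | 19 → 19 | 20 → 21 | 29 → 29 | 31 → 31 |
| Logit | 19 → 19 | 20 → 20 | 29 → 29 | 31 → 31 |
| Wald | 20 → 20 | 21 → 21 | 30 → 30 | 31 → 32 |
| Log | 20 → 20 | 21 → 22 | 30 → 31 | 32 → 32 |

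The count never moves by more than one event. As an example, the exact 97.5% bound at N = 141 is 19.42% for 18 events and 20.24% for 19, so 19 events fail at 20.2% and pass at 20.5%. If the true rate were 20.2%, the chance of passing would be P(X ≤ 18) = 1.5% under the first rule and P(X ≤ 19) = 2.6% under the second, against a nominal 2.5%.

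**The case against.** The addition error itself cannot be defended. 20.5% appears in current text both as a formula and in prose, so a fault in reading the PDF is unlikely. The case on the other side concerns weight.

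- **Power is weak evidence about which number was meant.** CIP Section 11 and SAP Section 6.6 attach the same 141 to at least 80% power at 0.05, which either null satisfies. The contrast of 141 with 134 also assumes that N is the smallest giving a full 92.0%; if power is rounded, 139 is enough at 0.202 (91.7%). This stands in part. The written sum, the 17.4% and the explicit 0.202 settle the point, and the power calculation supports them: under the test in Section 11.1, 0.205 would be reported as 94%.
- **The event counts depend on the methods chosen.** Exact and Wilson bounds are not Kaplan-Meier intervals, and full follow-up of 200 subjects sits badly with the CIP's own 29.5% allowance for loss. This stands for the detail of the table, which is illustrative. Zero or one event holds in every combination tried.
- **The conflict between 95% and 97.5% bounds matters more.** In the table it always moves the count, by one or two events. That is right, but it is a separate fault, and correcting the PG does not resolve it.
- **Nothing follows in practice.** No table, listing or figure named in the SAP reports the PG, so a repeated error in the final report is possible rather than certain. This stands, and it is why the point is minor.

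**Conclusion.** The concern holds as a minor documentation error. On the CIP's own inputs the PG is 20.2%; the printed 20.5% is 0.3 points too lenient and disagrees with the stated margin, the stated relative increase and the null in Section 11.1. The sample size is unaffected. The decision rule would have shifted by at most one amputation, assuming binomial data, complete 3-year follow-up and one of the interval methods tabulated. Because the SAP drops the primary test and the 3-year analysis, no reported result changes. The conclusion that 20.2% was intended rests on figures in the CIP alone.

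**What to change.** Replace 20.5% with 20.2% in both places in CIP Section 8, and state PG = 20.2% in CIP Section 11.2.2 and SAP Section 5, so that the number does not have to be traced back to its derivation. If a margin of 3.3 points was in fact intended, the CIP would have to say so and change the 3%, the 17.4% and the 0.202 to match; nothing in the text suggests this.

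If the CIP will not be amended after discontinuation, record the correction in SAP Section 12 and in the final report wherever the planned primary objective is described.

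The cost is wording only. The stated criterion becomes 0.3 points less favourable; the sample size, analyses and outputs stay as they are.

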## 8.1 PRIMARY ENDPOINT

The primary endpoint of the study is the overall performance of the devices (HOFFMANN® LRF SYSTEM, SALVATION™ EXTERNAL FIXATION SYSTEM, SALVATION™ FUSION BOLTS AND BEAMS, SALVATION™ 2 MIDFOOT NAIL, SALVATION™ 3DI PLATING SYSTEM, T2® ICF SYSTEM, and VALOR™ ANKLE FUSION NAIL Systems) measured as the 3-year amputation rate.

## 8.2 SECONDARY ENDPOINTS

The secondary performance endpoints are:

- Improvement in patient-reported function, and social interaction for quality of life via
  - EuroQuol five dimensions (EQ-5D-5L); and
  - Foot and Ankle Ability Measure (FAAM).
- Performance or survival of the device measured as the 5-year Amputation Rate

The secondary safety endpoints are:

- Adverse events through 5 years;
- Complications; and
- Investigator assessment of the implant including radiographic assessment of deformity correction, and fusion/consolidation time through 1 Year.
- Surgical Intervention

